3.1 Study Design

3.1.1 Study Phase

Phase 1/2.

3.1.2 Enrollment/Randomization

Subjects will be enrolled in a non-randomized, competitive multicenter, sequential enrollment manner with central subject registration. Subject enrollment and the safety of the combination regimen will be reviewed on an ongoing basis by an internal data safety monitoring panel (see Section 3.1.14, Safety Monitoring and Study Stopping Rules).

For each cohort in Phase 1, the start of the Cycle 1 Day 3 study drug administration (MEDI4736 + motolimod) for the first and second subject will be separated by at least 24 hours. All subjects in a cohort will have their safety data reviewed for DLTs as per Section 3.1.9, before proceeding with a cohort expansion or to a dose-escalated/de-escalated cohort (see section 3.1.7).

Per Amendment 1, the cohort at dose level 0b will be added to Phase 1. Depending on the timing of Amendment 1, dose level 0b cohort could be running concurrently with the cohort at dose level 0a, -1, or +1. Thus, subject enrollment will occur as follows:

- a) when only 1 cohort is open: sequential enrollment;
- b) when 2 parallel cohorts are open: preferential sequential enrollment into the cohort with the higher motolimod dose level or into the cohort with the higher MEDI4736 dose level if both cohorts have the same motolimod dose level.

PER Amendment 2, motolimod dosing will be discontinued for all subjects.

Subject enrollment will be centrally administered.

Enrollment in Phase 2 will begin after the MTD has been established in Phase 1.

3.1.3 Blinding/Unblinding

This is an open label study.

3.1.4 Subject Population

Subjects must have recurrent or persistent epithelial ovarian, fallopian tube, or primary peritoneal carcinoma with measureable disease (as defined by RECIST 1.1.) after first or second line platinum-based chemotherapy, for which treatment with PLD is indicated.

See Section 5 for complete eligibility criteria.

3.1.5 No. of Sites/Subjects

Approximately 6 to 9 sites; and 6 to 53 evaluable subjects are estimated for this study.

Phase 1: 6-18 evaluable subjects will be needed to identify the MTD.

Phase 2: 41 evaluable subjects, including the 6 subjects treated in Phase 1 at the MTD.

3.1.6 Sample Size and Statistical Considerations

Phase 1 of this trial will employ the 3+3 design as described in Section 3.1.7. The maximum tolerated dose (MTD) is defined as the highest dose for which fewer than 33% of subjects experience a dose-limiting toxicity (DLT).

Phase 2 of this trial will expand the Phase 1 cohort that was treated at the MTD. For the subject population to be enrolled, standard of care treatment with PLD alone has been reported to result in a 25% 6-months PFS rate. (47-50) A true 6-months PFS rate of $\geq 45\%$ in the current study, using motolimod + MEDI4736 with standard of care, would be of interest and represent a clinically meaningful improvement, while $\leq 25\%$ would be of no interest. Therefore, the study will test the hypotheses $H_0: p \leq 0.25$ versus $H_1: p \geq 0.45$, with p being the proportion of subjects who have survived and not progressed at 6 months, based on RECIST v1.1 criteria. Expansion of the Phase 1 MTD cohort to 41 evaluable subjects will yield 80% power to test the null hypothesis of 6-months PFS rate of $\leq 25\%$ against the alternative hypothesis of a PFS rate of $\geq 45\%$ at an alpha level of 0.05 (one-sided) based on exact test for single proportion.

PER Amendment 2, motolimod dosing will be discontinued for all subjects.

3.1.7 Treatment Arms and Treatment Schema

All subjects will be treated with pegylated liposomal doxorubicin (PLD) intravenously, MEDI4736 intravenously and motolimod (pre Amendment 2 only) subcutaneously during each 28-day cycle according to the treatment schedule below. On days with concurrent motolimod and MEDI4736 dosing, motolimod administration will occur 30-60 minutes after the end of the MEDI4736 infusion (pre Amendment 2 only).

PER Amendment 2, motolimod dosing will be discontinued for all subjects. At the time of Amendment 2, Phase 1 is completed, and Phase 2 will be initiated at the +1 dose level (PLD 40 mg/m², MEDI4736 1500 mg Q4W). Subjects who initiated treatment during Phase 1 will continue the trial at their respective doses levels for PLD and MEDI4736; however, motolimod will be discontinued.

PER Amendment 2 Treatment Schedule for Cohort at Dose Level 0a only	
DAY	CYCLES 1 – 12
1	Pegylated liposomal doxorubicin (IV)
3	MEDI4736 (IV)
17	MEDI4736 (IV)

PER Amendment 2 Treatment Schedule for all Subjects Except Cohort at Dose Level 0a	
DAY	CYCLES 1 – 12
1	Pegylated liposomal doxorubicin (IV)
3	MEDI4736 (IV)

Pre Amendment 2 Treatment Schedule for Cohort at Dose Level 0a only (see note below)		
DAY	CYCLES 1 – 3	CYCLES 4 – 12
1	Pegylated liposomal doxorubicin (IV)	Pegylated liposomal doxorubicin (IV)
3	MEDI4736 (IV) + Motolimod (SC)	MEDI4736 (IV) + Motolimod (SC)
10	Motolimod (SC)	n/a
17	MEDI4736 (IV) + Motolimod (SC)	MEDI4736 (IV) + Motolimod (SC)

[figure not shown]
Pre Amendment 2 Treatment Schedule for all Subjects Except Cohort at Dose Level 0a		
DAY	CYCLES 1 – 3	CYCLES 4 – 12
1	Pegylated liposomal doxorubicin (IV)	Pegylated liposomal doxorubicin (IV)
3	MEDI4736 (IV) + Motolimod (SC)	MEDI4736 (IV) + Motolimod (SC)
10	Motolimod (SC)	n/a
17	Motolimod (SC)	n/a

Phase 1 Dose escalations and de-escalations for the determination of the MTD (or highest tolerable dose tested) will be performed based on the available dose levels and the respective rules for a standard 3 + 3 study design, as per Dose Level Table and Schema below:

Dose Level Table			
Dose Level	Pegylated liposomal doxorubicin [mg/m² IV]	MEDI4736 [IV]	Motolimod [mg/m² SC] Pre Amendment 2 only*
-1	40	450 mg Q4W	2.0
0a (Starting Level)	40	3 mg/kg Q2W (equivalent to 450 mg Q4W)	2.5
0b	40	1500 mg Q4W**	2.0
+1	40	1500 mg Q4W**	2.5

Q2W = every 2 weeks; Q4W = every 4 weeks
 **Note for fixed dose of 1500 mg MEDI4736: If a subject's body weight drops to ≤ 30 kg while on the study, the MEDI4736 dose will be weight based as long as the subject's body weight remains ≤ 30 kg. See Section 6.3.3.2.
 *PER Amendment 2, motolimod dosing will be discontinued for all subjects

Note: Per Amendment 1, dose level 0 was renamed as 0a, and dose level 0b was added to Phase 1. Depending on the timing of Amendment 1, dose level 0b cohort could be running concurrently with the cohort at dose level 0a, -1, or +1. The dosing for the cohort in dose level 0a will continue per the protocol prior to Amendment 1 (i.e., MEDI4736 at 3 mg/kg Q2W); however, escalation or de-escalation dosing will be conducted according to Amendment 1.

For detailed definitions of DLT and MTD see Section 3.1.9.

Phase 2 subjects will be treated at the MTD level determined in Phase 1. See Sections 3.1.5 and 3.1.6 for the number of subjects to be enrolled.

Subjects will be followed on study for 90 days after the last drug administration and off-study every 3 months thereafter for 3 years from initiation of treatment (see Section 3.1.16).

3.1.8 Dosing Adjustments, Delays and Discontinuations

PER Amendment 2, motolimod dosing will be discontinued for all subjects.

Dose adjustment and management guidelines for toxicity related to the standard PLD regimen, motolimod, and MEDI4736 are outlined in Sections 8.2, 8.3, 8.4, respectively.

In the event of a delay in PLD dosing due to drug-related toxicity, doses of motolimod and MEDI4736 should also be delayed, so that the relative timing of the administration of each drug within each cycle is not altered. That is, the administration of PLD always constitutes cycle Day 1, and the dose dates of motolimod and MEDI4736 are determined relative to this date (see Section 3.1.7). Note that delays in the dosing of motolimod or MEDI4736 due to drug-related toxicity should not delay the 28-day dosing cycle of PLD, if possible. Likewise, any delay in MEDI4736 should not delay the administration of motolimod, and vice versa.

If PLD has to be discontinued due to PLD-related toxicities, the treatment with motolimod and/or MEDI4736 may continue, provided that the subject had received at least 2 doses of PLD (i.e., 2 cycles).

Irrespective of delay(s) in the dosing of the combination treatment, the disease assessments (CT, MRI) should not be delayed and must be conducted on the days originally scheduled, as calculated from the first study dose of PLD (Cycle 1 Day 1).

If a toxicity occurs that requires toxicity management in accordance with the toxicity management guidelines referenced above, and the toxicity causing drug can be clearly identified, then the respective guideline should be followed. If the toxicity causing drug cannot be identified, then the more conservative guideline should be followed.

3.1.9 DLT and MTD

PER Amendment 2, motolimod dosing will be discontinued for all subjects.

DLTs will be observed over a period of the first cycle including the pre-dose assessment for Cycle 2, defined as the “DLT Evaluation Period”. The decisions for dose escalations, de-escalations and MTD, as described in Section 3.1.7, will primarily be based on the number of subjects with DLTs occurring during the DLT Evaluation Period. DLTs occurring outside the DLT Evaluation Period will also be evaluated and may impact such decisions.

DLTs are defined as any adverse events that are possibly, probably, or definitely related to the administration of MEDI4736, motolimod or PLD, and fulfill any of the following criteria:

1. Any Grade \geq 3 colitis, pneumonitis, neurological event, or uveitis.
2. Any Grade 2 pneumonitis, neurological event, or uveitis with the following exception:
 - Grade 2 pneumonitis, neurological event, or uveitis that downgrades to Grade \leq 1 within 3 days after onset, whereby maximal supportive care, including systemic corticosteroids, is permitted.
3. Any *other* Grade \geq 3 toxicity, with the following exceptions:
 - Grade \geq 3 PLD-related toxicities, manageable according to the dose modification instructions in the package insert/product information (see Section 8.2.)
 - Grade 3 irAEs (see definition below) that downgrade to Grade \leq 2 within 3 days, or to Grade \leq 1 or baseline within 14 days after onset, whereby maximal supportive care, including systemic corticosteroids, is permitted.
 - Grade 3 endocrinopathy that becomes asymptomatic when managed with or without systemic corticosteroid therapy and/or hormone replacement therapy.
 - Grade 3 inflammatory reaction attributed to a local antitumor response (e.g., inflammatory reaction at sites of metastatic disease, lymph nodes, etc.).
 - Grade 3 fatigue for \leq 7 days.
 - Grade 3 infusion-related reaction (first occurrence and in the absence of steroid prophylaxis) that resolves within 6 hours with appropriate clinical management.
 - Liver transaminase elevation \leq 8 times ULN that downgrades to Grade \leq 2 (\leq 5 times ULN) within 7 days after onset, whereby maximal supportive care, including systemic corticosteroids, is permitted.
 - Total bilirubin \leq 5 times ULN that downgrades to Grade \leq 2 (\leq 3 times ULN) within 7 days after onset, whereby maximal supportive care, including systemic corticosteroids, is permitted.
 - Grade \geq 3 neutropenia that (1) is not associated with fever or systemic infection, (2) does not require medical intervention, and (3) improves to Grade 2 within 7 days.
 - Grade 3 or Grade 4 lymphopenia.

- Grade 3 thrombocytopenia that (1) is not associated with clinically significant bleeding, (2) does not require medical intervention, and (3) improves to Grade 2 within 7 days.
- Isolated Grade 3 electrolyte abnormalities that are not associated with clinical signs or symptoms and are reversed with appropriate maximal medical intervention within 3 days.
- Any pre-existing laboratory abnormality that deteriorates to Grade 3/4, but where the increment of deterioration is considered not clinically significant by both Investigator and Sponsor.

Immune-related AEs (irAEs) are defined as AEs of immune nature (i.e., inflammatory) in the absence of a clear alternative etiology. In the absence of clinical abnormality, repeat laboratory testing will be conducted to confirm significant laboratory findings prior to designation as a DLT.

While rules for adjudicating DLTs are specified above, an AE that is Grade < 3 or listed as exempt above may also be defined as DLT after consultation with the Sponsor and Investigators, based on the emerging safety profiles of MEDI4736 and motolimod, and in combination with PLD. Likewise, subjects who become not evaluable for DLT, because they discontinued or interrupted treatment due to toxicities other than DLTs, may be counted as DLT subjects, if the toxicities cannot be managed in accordance with the dosing modifications described in Section 3.1.8.

Subjects who experience a DLT will be discontinued from study therapy and will enter the On Study Follow-up phase of the study (see Sections 3.1.16 and 3.2). However, if it is in the best interest of the subject, the Investigator and Sponsor may agree to continue treatment, possibly at a lower dose level.

The MTD of combination treatment is defined as the highest dose of MEDI4736 + motolimod + PLD studied, for which the observed incidence of DLT is less than 33% (based on n=6).

3.1.10 Subject Withdrawal from Treatment or Study

A subject will be **withdrawn from study treatment** for any of the following reasons:

1. Withdrawal of consent for further treatment.
2. Pregnancy or intent to become pregnant.
3. Dose-limiting toxicity at any time (see Section 3.1.9 for definition of DLT and permitted continuation).
4. Confirmation of progressive disease by irRECIST criteria requiring alternative treatment.
5. Significant protocol violation or noncompliance that, in the opinion of the Investigator or Sponsor, warrants withdrawal.
6. Development of intercurrent, non-cancer related illnesses or complications that prevent either continuation of therapy or regular follow-up.
7. Best medical interest of the subject (at the discretion of the Investigator)

Discontinuation from receiving study treatment does not mean that the subject is withdrawn from the study. If feasible, subjects who are withdrawn from study treatment should enter the On Study Follow-Up, followed by the Post Study Follow-up (see Sections 3.1.16 and 3.2).

Subjects who begin other anti-cancer therapy should immediately be considered off-study and proceed to the Post Study Follow-up (see Section 3.1.16).

A subject will be **withdrawn from the study** for the following reasons:

1. Best medical interest of the subject at the discretion of the Investigator.
2. Initiation of alternative anti-cancer therapy including marketed or another investigational agent.
3. Withdrawal of consent for all follow-up.
4. Lost to follow-up.
5. Death

General subject withdrawal criteria are outlined in the Administrative, Legal and Ethical Requirements section of the protocol (see Section 7.2.6).

See also Sections 8.2, 8.3, and 8.4 for subject withdrawal from treatment due to necessary dosing interruptions or discontinuations.

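### Section 8.4.2.1 lets MEDI4736 resume or continue after four kinds of related DLT without the Investigator–Sponsor agreement that Sections 3.1.9 and 3.1.10 require

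*Protocol*

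**What the plan says.** **Withdrawal rule.** Protocol 3.1.10, item 3, ends study treatment for "Dose-limiting toxicity at any time (see Section 3.1.9 for definition of DLT and permitted continuation". Section 3.1.9 says the same: "Subjects who experience a DLT will be discontinued from study therapy and will enter the On Study Follow-up phase of the study". There is one way out: if it serves the subject, "the Investigator and Sponsor may agree to continue treatment, possibly at a lower dose level". Since Amendment 2 removed motolimod, study therapy means PLD and MEDI4736. Nothing limits the rule to Cycle 1 or to Phase 1. Item 3 has no time limit, and 3.1.9 says DLTs after the first cycle are also evaluated.

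**DLT definition (3.1.9).** An adverse event at least possibly related to a study drug is a DLT if it meets one of three criteria:
- Grade 3 or higher "colitis, pneumonitis, neurological event, or uveitis".
- "Any Grade 2 pneumonitis, neurological event, or uveitis with the following exception", the exception being a fall to Grade 1 or lower within 3 days.
- Any other Grade 3 or higher toxicity outside a list of exceptions. One covers Grade 3 immune-related events that fall to Grade 2 or lower within 3 days, or to Grade 1 "or baseline within 14 days after onset, whereby maximal supportive care, including systemic corticosteroids, is permitted". Another is "Grade 3 endocrinopathy that becomes asymptomatic when managed with or without systemic corticosteroid therapy".

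**Dosing rule.** Section 8.4.2.1 tells sites when to hold, restart or permanently stop MEDI4736, by grade and event. Section 3.1.8 and the head of 8.4 both direct sites there: where "the toxicity causing drug can be clearly identified, then the respective guideline should be followed". Neither adds an exception for DLTs.

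**The concern.** The protocol has two sets of instructions for the same subject. Under 3.1.9 and 3.1.10 a related DLT stops both drugs unless Investigator and Sponsor agree otherwise. Under 8.4.2.1 some of the same events lead to a hold followed by restart, or to no hold at all, on the site's decision alone.

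At stake is whether a subject is re-exposed to a checkpoint inhibitor after a serious immune toxicity without the joint decision that the protocol treats as the safeguard. Sites could also handle identical events differently while each remains within the text.

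**Working it through.** No arithmetic applies. The check sets the two rules side by side, event by event, for events judged related. Section 3.1.9 counts days from onset. Section 8.4.2.1 does not say when its 30 and 60 days start. Onset is assumed here; a later start would lengthen the overlap, not remove it.

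| Event | Under 3.1.9 | Under 8.4.2.1 |
|---|---|---|
| 1. Grade 3 neurological event or uveitis | Always a DLT | Restart once at Grade 1 or lower and any steroid taper has ended; limit 30 days for neurotoxicity, 60 days for uveitis (general rule, as it has no row of its own) |
| 2. Grade 2 neurological event or uveitis not at Grade 1 or lower within 3 days | DLT | Same restart rule and limits; for sensory neuropathy even the hold is left to the Investigator |
| 3. Other Grade 3 immune-related event, not at Grade 2 or lower within 3 days and at Grade 1 or baseline only after day 14 | DLT | Restart allowed up to day 60 (day 30 for rash) |
| 4. Grade 4 endocrinopathy | DLT, because the exception stops at Grade 3 | Grade 2 retreatment rule applies: retreat if controlled and clinically stable |

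**Taken out because 8.4.2 stops MEDI4736 permanently:**
- Grade 3 pneumonitis, enterocolitis, myocarditis and raised creatinine.
- Grade 3 hepatitis not resolved within 14 days.
- Neuromotor syndromes with respiratory insufficiency or unstable autonomic function.
- Bullous rash of any grade.
- Grade 3–4 infusion reactions (8.4.2.2).

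**Taken out of kind 3 because 3.1.9 exempts them:** Grade 3 endocrinopathy that becomes asymptomatic under management, and Grade 3 inflammatory reactions attributed to a local antitumor response. Neither exemption has a 14-day limit.

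**Conditional:**
- Asymptomatic amylase or lipase rises. Section 8.4.2.1 allows MEDI4736 to continue after a negative pancreatitis work-up. However, 4.2.1 records only clinically significant laboratory abnormalities as adverse events, and 3.1.9 asks for repeat testing first.
- Grade 3 non-immune events under 8.4.2.3. These conflict only if no 3.1.9 exception covers them.

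Count: 4 clear + 2 conditional = 6 kinds of event.

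**Is precedence stated anywhere?**
- The last line of 3.1.10 points to 8.2, 8.3 and 8.4 as further sources on withdrawal but does not rank them.
- The fallback in 3.1.8 to the more conservative guideline applies only when the causal drug is unknown.
- The extra list of permanent-stop reasons in 8.4.2.1 does not include a DLT.
- DLT status limits restart in one place in 8.4.2: Grade 2 pneumonitis or interstitial lung disease and myocarditis.
- Sponsor consultation appears once, for Grade 4 isolated laboratory results (8.4.2.3).

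**PLD.** Sections 3.1.8, 8.2 and 8.4.2 say a MEDI4736 hold should not delay other drugs. A subject managed under 8.4.2.1 can therefore receive PLD during the hold, although 3.1.9 has stopped study therapy.

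**The case against.** The strongest reply is that both rules can be obeyed in order. Section 3.1.10 decides who stays on treatment, and 8.4.2 governs dosing for those who do. A withdrawn subject has no next scheduled dose, so nothing in 8.4.2 waives the agreement. The wording lends some support: 3.1.9 and 3.1.10 are mandatory, while the 8.4.2.1 rules are often general or permissive. The one DLT proviso in 8.4.2.1 also suggests that the drafters saw DLT status as limiting restart.

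This reading is possible, but no text states it. If it were understood throughout, the single proviso would be unnecessary; placed where it is, it makes silence elsewhere look like permission. An event classed as immune-related, with no clear other cause, will nearly always be at least possibly drug-related. On the sequential reading, the restart rule for Grade 3 neurotoxicity would have almost no use without Sponsor agreement.

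The second reply is that the Sponsor will hear of these events anyway. The safety panel, which includes the Sponsor's Medical Monitor, reviews safety continuously (3.1.14, 4.2). Neurotoxicity, endocrine disorders and uveitis are events of special interest (7.1.8). Serious events are reported within 24 hours (7.1.6). Recurrence of a Grade 3 related event after restart stops MEDI4736 permanently (8.4.2.1). This stands as mitigation, so a reader should not infer that re-dosing would go unseen by the Sponsor. None of these steps, however, requires agreement before the next dose, and a non-serious Grade 2 neuropathy or uveitis need not trigger SAE reporting or a stopping-rule review.

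**Conclusion.** The inconsistency is real and should be corrected. For four kinds of related DLT, 8.4.2.1 permits MEDI4736 to resume or continue without the agreement required by 3.1.9; two more kinds conflict only when they qualify as DLTs. The conclusion rests on the events being judged at least possibly related, and on the absence of any precedence statement.

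Three stronger readings are tempting but unsupported:
- A reader might infer that 8.4.2 as a whole contradicts the withdrawal rule. It does not: many of its rules are as strict or stricter, and several Grade 3 events are not DLTs.
- A reader might infer that re-dosing follows within one dosing interval (28 days, or 14 at level 0a). Under 3.1.8 a PLD delay for drug-related toxicity also delays MEDI4736, so no time bound holds.
- A reader might infer a bias in the 6-month PFS result, since the binomial sensitivity analysis in SAP 3.8.1 counts treatment discontinuation as progression. The documents give no rates for these events, so neither a number of subjects nor a shift can be stated, and no effect on the efficacy result is claimed.

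**What to change.** Add the following to 3.1.8 and to the head of 8.4.2, with a cross-reference from item 3 of 3.1.10:

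*Section 3.1.9 takes precedence over Sections 8.2 and 8.4. If an event meets the DLT criteria in Section 3.1.9, in Phase 1 or Phase 2, no further PLD or MEDI4736 is given until the Investigator and Sponsor have agreed under Section 3.1.9 to continue, stating which drugs continue and at what dose; the restart conditions in Section 8.4.2 then apply.*

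The text must name PLD, because a condition on MEDI4736 alone would leave PLD running during the hold. Routine PLD management is unaffected: 3.1.9 already exempts PLD-related toxicities that can be managed by dose modification. The existing proviso for Grade 2 pneumonitis and myocarditis agrees with the new text and can stay.

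The cost is a short protocol amendment, one Sponsor consultation per such event, and a possible short PLD delay while agreement is obtained. No extra subjects, procedures or SAP changes are needed.
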